## LIST OF IN-TEXT TABLES

## ABBREVIATIONS AND SPECIALIST TERMS

ADME	absorption/distribution/metabolism/excretion
AE	adverse event
AUC 0-t	area under the curve from time zero to time t
BP	blood pressure
CGH	comparative genomic hybridization
CI	confidence interval
CISH	chromogenic in situ hybridization
C max	maximum concentration
CR	complete response
CRF	case report form
CSR	clinical study report
CTCAE	common terminology criteria for adverse events
CTCs	circulating tumor cells
DMC	data monitoring committee
DNA	deoxyribonucleic acid
DCR	disease control rate
DR	duration of response
ECG	electrocardiogram
ECHO	echocardiogram
ECOG	Eastern Cooperative Oncology Group
eCRF	electronic case report form
e.g.	exempli gratia (for example)
EOS	end of study
ER+	estrogen receptor positive
FACT-B	Functional Assessment of Cancer Therapy- Breast
FGF	fibroblast growth factor
FGFR	fibroblast growth factor receptor
FISH	fluorescence in situ hybridization
HER2	human epidermal growth factor receptor 2
i.e.	id est (that is)
ICF	informed consent form
kg	kilogram
MUGA	multi gated acquisition scan
mg	milligram
NA	not applicable
NCI	National Cancer Institute
NE	not evaluable
NGS	next generation sequencing
ORR	objective response rate
OS	overall survival
qPCR	quantitative polymerase chain reaction

QT c B	QT interval corrected using Bazette's method
QT c F	QT interval corrected using Fridericia's method
PD	progressive disease
PFS	progression free survival
РК	pharmacokinetics
POPPK	population pharmacokinetics
PR	partial response
PRO	patient reported outcomes
RECIST	response evaluation criteria in solid tumours
SAE	serious adverse event
SAP	statistical analysis plan
SAS	statistical analysis system (company)
SD	stable disease
SI	Systeme International
$t_{1/2}$	elimination half-life
t max	time to maximum concentration
VEGF	vascular endothelial growth factor
VEGFR	vascular endothelial growth factor receptor
WHO	World Health Organization

## **1** INTRODUCTION

This document describes the statistical analyses and data presentations to be performed for Clovis Oncology protocol CO-3210-025 "A Phase 2, randomized, open-label, multicenter, safety and efficacy study of oral lucitanib in patients with FGF aberrant metastatic breast cancer". This statistical analysis plan (SAP) provides a comprehensive and detailed description of the strategy, rationale, and statistical techniques to be used to assess the efficacy and safety of lucitanib administered orally to patients with metastatic breast cancer.

The purpose of the SAP is to ensure the credibility of the study findings by specifying the statistical approaches to the analysis of study data prior to database lock for the final analysis. This SAP provides additional details concerning the statistical analyses that were originally outlined in the protocol.

All statistical analyses detailed in this SAP will be conducted using SAS® Version 9.3 or higher.

## **2** OVERALL STUDY DESIGN, OBJECTIVES, AND ENDPOINTS

## 2.1 Study Objectives and Endpoints

From the original protocol through amendment 5 of the protocol, there were three cohorts planned for which objectives and endpoints where defined. Cohort A was to have a starting dose of 10 mg daily of lucitanib; Cohort B was to have a starting dose of 15 mg daily of lucitanib; and Cohort C was added in amendment 2 and was to initially receive 15 mg daily of lucitanib. However, the major protocol amendment #4 discontinued the use of 15 mg as an initial starting dose thereby changing the initial starting dose for all subsequently enrolled patients in Cohort C to 10 mg of lucitanib as well as advising all investigators with patients receiving 15 mg lucitanib to dose reduce to 10 mg. Due to the significant changes to the protocol defined Cohorts and corresponding objectives and endpoints throughout the study, Table 1 below will only indicate those objectives and endpoints outlined in amendment #5 of the protocol.

Table 1. Primary, Secondary, and Exploratory Objectives and End	points
---	--------

Primary Objectives	Primary Endpoints
To estimate the anti-tumor efficacy of oral single-agent lucitanib as measured by investigator assessed PFS, when administered to patients with FGFR1 - or 11q-amplified breast cancer after failure of currently available standard therapies	Progression-free Survival (PFS) per RECIST Version 1.1 as determined by the investigator

Secondary Objectives	Secondary Endpoints	
To estimate the anti-tumor efficacy of oral single-agent lucitanib as measured by investigator assessed PFS, when administered to patients with FGFR1 - or 11q-amplified breast cancer after failure of currently available standard therapies	
 
ORR according to RECIST Version 1.1
 
DR and DCR according to RECIST Version 1.1
 
OS
 
	
To estimate patient-reported outcomes (PRO) following treatment with lucitanib	Change from baseline in PRO using the Functional Assessment of Cancer Therapy- Breast (FACT-B) questionnaire	
To evaluate the safety and tolerability of lucitanib	Treatment emergent AEs, laboratory abnormalities, physical examinations including vital signs and electrocardiogram (ECG) abnormalities	
To assess the comparative pharmacokinetics (PK) of the lucitanib tablet formulation with the lucitanib capsule formulation	PK parameters including area under the concentration curve from time zero to time t (AUC 0-t ), maximum concentration ( $C_{max}$ ), time to maximum concentration ( $t_{max}$ ), elimination half-life ( $t_{1/2}$ ), volume of distribution at steady state (V SS /F), and total plasma clearance (Cl/F) for lucitanib, if data allow	
Exploratory Objectives	Exploratory Endpoints	
To explore tumor tissue and blood-based biomarkers that may be predictive of response or primary resistance to treatment with lucitanib	• Concordance of tumor tissue FGFR1 and 11q amplification assessed across different technical platforms (fluorescence in-situ hybridization [FISH], Next Generation Sequencing [NGS], comparative genomic hybridization [CGH], chromogenic in-situ hybridization [CISH], quantitative polymerase chain reaction [qPCR], or circulating tumor cells [CTCs/ctDNA])	
	• Exploration of different cut-off values for determining FGFR1 and 11q amplification in tumor tissue by FISH and correlation with clinical efficacy	
	• Ribonucleic acid (RNA) expression of FGFR1 , FGF3/4/19, and additional FGF family members; correlation with FGFR1 and 11q amplification status and clinical efficacy	

	• Protein expression of FGFR1 as determined by immunohistochemistry (IHC) in tumor tissue; correlation with FGFR1 amplification status
	Genomic analysis of circulating tumor DNA (ctDNA)
To explore blood-based pharmacodynamics (PD) biomarkers of lucitanib activity	• PD biomarker analysis measurement of circulating plasma biomarker levels including but not limited to FGF-2, FGF-23, sVEGFR1, VEGF-A, sCSF-1R, and CSF-1
	• Pharmacogenomic analysis of variations in genes encoding proteins involved in absorption/distribution/ metabolism/excretion (ADME)

• Participation in the PK sub study will be optional for patients participating in Cohort A

Participation in the PK sub study will be required for patients participating in Cohort C until enrollment of the PK sub study is completed

## 2.2.1 Screening Period

FGF-amplified (Cohort A) and FGF non-amplified (Cohort C) patients will undergo screening assessments within 28 days of the first dose of lucitanib.

Cohort A or C patients enrolled into the PK sub-study must undergo screening assessments within 21 days of the first dose of lucitanib, i.e., prior to Day –7.

For all patients, AEs will be assessed from the time of first dose of lucitanib through 28 days after the last protocol-specified treatment administration. Study-procedure-related AEs that occur after signing of the Informed Consent Form (ICF) and before administration of lucitanib will also be collected as AEs. AEs that occur after signing of the ICF and before lucitanib should be captured on the Medical History eCRF.

#### 2.2.2 Treatment Period

Lucitanib will be administered once daily and swallowed with water. Patients should take lucitanib at approximately the same time each day, on an empty stomach, at least 2 hours before and 2 hours after a meal (fasting window is a total of four hours). Treatment with lucitanib is continuous but cycles will be defined as 28 days in duration. Dosing will be delayed or reduced according to protocol-specified toxicity criteria. Protocol-specified treatment will continue until there is clinical tumor progression or unacceptable toxicity.

Patients will undergo serial assessments for anti-tumor efficacy, drug safety, and PROs. Tumor scans will be acquired by the investigative site and evaluated locally for patient treatment decisions. Electronic copies of tumor scans will be uploaded to a central radiological vendor and held for review, if deemed necessary. Sparse blood sampling for POPPK analyses will be conducted in all patients treated with lucitanib. Serial blood sampling for PD evaluation will be conducted. Local laboratories will be used for standard hematology and chemistry tests. Echocardiogram (ECHO)/multiple-gated acquisition (MUGA) will be done locally. ECGs will be stored and may be analyzed centrally. Patients will be asked to self-monitor their BP at least two times per week and instructed to contact the study site in the event of a BP reading equal or above 160 mmHg systolic and/or greater than 100 mmHg diastolic.

Patients with SD or better after their Cycle 6 scan will continue to have tumor scans every  $12 \pm 1$  weeks until tumor progression. After discontinuation of protocol-specified treatment, subsequent specific anticancer therapy used at the investigator's discretion will be recorded. Patients will be encouraged to undergo an optional post-treatment tumor biopsy at time of progression and before subsequent-line therapy is initiated.

## 2.2.3 End-of-Study

All patients should return to the clinic for end-of-study assessments 28 ( $\pm$ 7) days after the last dose of lucitanib has been administered.

The trial will be completed when all enrolled patients have discontinued treatment and completed the end-of-study follow-up visit.

### 2.2.4 Long Term Follow-Up

All patients will be followed at approximately two monthly intervals to determine survival status, until death or sponsor decision to end the trial, whichever comes first.

#### 2.2.5 Study Schema

The study schemas in Figure 1 summarizes the updated treatment design of the study.

## Figure 1: Study Schema

aUp to 20 patients enrolled into Cohort C will participate in a PK sub study. Patients enrolled into Cohort A should also be considered for inclusion in the PK sub study at selected sites.

## 2.2.6 Number of Patients and Sites

*FGFR1*-amplified and 11q-amplified patients will be enrolled\* as follows:

• Cohort A (10 mg): approximately 80 patients

FGF non- amplified patients will be enrolled into Cohort C as follows:

• Cohort C (10 mg): up to 40 patients

\*1:1 randomization to Cohorts A and B was removed with Amendment #4.

Up to 20 patients will participate in a PK sub study to assess the comparative PK of the lucitanib tablet formulation with the lucitanib capsule formulation. Additional patients may be added to the PK sub-study to account for patients with incomplete PK sampling profiles at either Day –7 or Day 1, or to account for higher than expected variability in the observed PK profiles.

Enrollment into the PK sub study may only be opened at a limited number of sites based on study requirements and operational feasibility.

Patients in Cohorts A or C will be enrolled in the PK sub study at participating sites, as follows:

- Participation in the PK sub study will be optional for patients participating in Cohort A
- Participation in the PK sub study will be required for patients participating in Cohort C until enrollment of the PK sub study is completed

There will be approximately 30–40 investigative sites in the United States. All patients enrolled in Cohort C are required to participate in the PK sub study. Accrual to Cohort C will

be limited to 10-15 sites participating in the PK sub study, until enrollment in the sub study has been filled.

## **3** SAMPLE SIZE

Under the original protocol, approximately 160 patients were to be randomized 1:1 to the 10 mg and 15 mg daily dosing groups (Cohorts A and B).

Under protocol amendment 5, the following are the revised sample size considerations.

Up to 200 patients will be enrolled.

A total of at least 80 patients in the 10 mg arm is sufficient to reliably estimate the median PFS and 6 month PFS rate in these heavily pre-treated patients. An observed median PFS greater than 4 months or a 6-month PFS rate of at least 40% will be sufficient to consider the 10 mg dose group worthy of further study. Therefore, with at least 80 patients treated at 10 mg, the width of the 90% confidence interval for the 6 month PFS rate will be less than  $\pm 10\%$ , so that if the observed 6 month rate is 50% then the lower limit on the confidence interval will be greater than 40%.

The treatment effect in Cohort C (biomarker negative sub-group) is not expected to be as large as in Cohorts A and B; however, the same target of 40% will be used to evaluate Cohort C. With 40 patients, the width of the 90% confidence interval for the 6 month PFS rate will be less than  $\pm 15\%$ , so that if the observed 6 month rate is less than 25% then the upper limit on the confidence interval will be less than 40%, which is evidence that subsequent studies of 10 mg should exclude biomarker negative patients.

## **4** GENERAL ANALYSIS CONSIDERATIONS

Due to significant changes to the study design throughout the study, all summaries of data will be presented by initial study drug dose level (10 mg, 15 mg) regardless of a patient's enrollment into study cohorts A, B, and C. Initial dose groups will be referred to as treatment groups (10 mg, 15 mg). An overall column combining all patients from both treatment groups will be included in the data summaries, where applicable.

Quantitative variables will be summarized using descriptive statistics (N, mean, standard deviation, median, minimum, and maximum) and/or frequency and percentages for medically relevant categories. Categorical variables will be presented using frequencies and percentages. Exact 95% confidence intervals may be presented for frequencies.

All data will be used to their maximum possible extent but without any imputations for missing data.

All statistical analyses will be conducted with the statistical analysis software (SAS®) System, Version 9.3 or higher.

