## **12** EFFICACY ANALYSIS

#### **12.1** Primary Efficacy Analysis

Kaplan-Meier methodology will be used to summarize the time to event variables including the estimated 50th (median) percentile by treatment group.

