#### 12.2.4 PK Sub Study (Cohort C)

Comparative PK parameters will include  $AUC_{0-t}$ ,  $C_{max}$ ,  $T_{max}$ ,  $T_{1/2}$ ,  $V_{SS}/F$ , and Cl/F for lucitanib and will be determined using noncompartmental methods.  $AUC_{0-t}$  will be calculated using the trapezoid rule. The PK parameters will be compared between the tablet and the capsule formulations.

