## **15 PATIENT REPORTED OUTCOMES**

PROs will be measured using the FACT-B questionnaire in all patients with both a baseline assessment and at least one post-baseline assessment.

The baseline PRO measurement will be defined as the last value prior to or on the day of the first dose of lucitanib. The on-treatment period will be defined as the day after the first dose of lucitanib to 28 days after the last dose of protocol-specified treatment. PRO measurements collected during the on-treatment period will be included in the summary tables.

The summary of PRO data will include descriptive statistics (N, mean, standard deviation, median, minimum, and maximum) of the maximum, minimum, and last value during the on-treatment period. Summaries using descriptive statistics of the change from baseline to the maximum, minimum, and last value during the on-treatment period will also be given by relevant cohort.

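### The SAP plans PFS by starting dose only, so it yields no PFS estimate for the amplified patients of the primary objective and none for the Cohort C rule it keeps

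*SAP*

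**What the plan says.** - **Objective.** SAP Section 2.1, Table 1, gives the primary objective as estimating investigator-assessed PFS in patients with FGFR1- or "11q-amplified breast cancer after failure of currently available standard therapies".
- **Rules.** SAP Section 3 keeps two. For 10 mg: "An observed median PFS greater than 4 months or a 6-month PFS rate of at least 40% will be sufficient" to take that dose group forward. For Cohort C, an observed 6-month rate below 25% in 40 patients would put the 90% upper limit below 40%, "which is evidence that subsequent studies of 10 mg should exclude biomarker negative patients".
- **Grouping.** SAP Section 4 says "all summaries of data will be presented by initial study drug dose level (10 mg, 15 mg) regardless of" the cohort in which a patient was enrolled. It gives a reason: the design changed substantially during the trial.
- **Output.** SAP Section 12.1 summarises time-to-event variables by Kaplan-Meier, "including the estimated 50th (median) percentile by treatment group". Section 12.1.1 adds only the PFS definition and censoring.
- **FGF status.** It appears as a baseline characteristic in SAP Section 8.2. The Efficacy Population as redefined in SAP Section 5 has no FGF criterion.
- **Protocol.** Section 11.2.1 commits to comparing FGFR1-amplified, 11q-amplified and non-amplified patients, at 10 mg and for both doses. Section 11.2.4 commits to 6- and 12-month Kaplan-Meier rates, and says only that efficacy may be shown by cohort.

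**The concern.** A programmer who follows SAP Sections 4 and 12.1 literally produces PFS for a 10 mg column, a 15 mg column and an overall column. Each can mix amplified and non-amplified patients, because Cohort C patients started at 15 mg under Amendment 3 and at 10 mg under Amendment 4 (SAP Section 2.2). None of these columns estimates the quantity in the primary objective. The question that Cohort C was added to answer, whether later 10 mg studies should leave out non-amplified patients, gets no planned PFS result.

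SAP Section 3 itself expects a smaller effect in Cohort C, so the pooled 10 mg figure would be expected to understate PFS in amplified patients. If the FGF-specific estimates are added only after the data have been seen, they lose the prespecification that SAP Section 1 gives as the document's purpose.

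**Working it through.** **1. What each retained statement needs, against what is planned.**

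| Retained in the SAP | Estimate needed | Planned in SAP Section 12 |
|---|---|---|
| Primary objective (2.1) | PFS in amplified patients | No; dose columns only |
| 10 mg rule (3) | Median or 6-month rate at 10 mg | Median yes, in a column of mixed FGF status; rate not named |
| Cohort C rule (3) | 6-month rate with 90% CI in non-amplified patients | No |

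**2. Section 3's precision statements reproduce.** Wald 90% limits are p ± 1.645 × √(p(1−p)/n), with no censoring before 6 months.
- n = 80, p = 0.50: 1.645 × √(0.25/80) = 0.092, so 40.8% to 59.2% (exact lower limit 40.3%). The stated lower limit above 40% holds, by under one point.
- n = 40, p = 0.25: 1.645 × √(0.1875/40) = 0.113, so the upper limit is 36.3% (exact 38.7%). The stated upper limit below 40% holds.

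Both statements concern a 6-month rate, and the second needs Cohort C on its own.

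**3. Illustration of pooling at 10 mg.** Assumptions: 80 amplified patients at 50%, and m non-amplified patients at 25%. These rates are the values Section 3 uses to illustrate precision; they are not predictions. The documents do not give m. It can lie between 0 and 40.

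Pooled rate = (80 × 0.50 + m × 0.25)/(80 + m).
- m = 20: 45/100 = 45.0%. Lower limit 0.450 − 1.645 × √(0.2475/100) = 36.8%.
- m = 40: 50/120 = 41.7%. Lower limit 0.417 − 1.645 × √(0.2431/120) = 34.3%.
- Amplified patients alone: 50.0%, lower limit 40.8%.

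**4. Does the 10 mg decision change?** The rule is met by the median or by the rate. Under exponential PFS a 40% 6-month rate corresponds to a median of 6 × ln 2/(−ln 0.40) = 4.54 months, so passing on the rate implies passing on the median. The same held in a mixture of two exponentials with amplified rates of 30% to 60%, non-amplified rates from 5% up to the amplified rate, and m from 0 to 40: no case had a rate of at least 40% with a median of 4 months or less. In step 3 with m = 40, the pooled median is 4.70 months and the rule is still met.

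**5. Precision of a separate non-amplified column** at an observed 25%: the 90% upper limit is 38.0% (Wald) to 41.2% (exact, interpolated) with 30 patients, and 40.9% to 45.6% with 20.

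**The case against.** **The pooling is deliberate and explained.** SAP Section 4 gives its reason, and cohort labels are awkward once Cohort C spans two starting doses. This stands as a reason for dropping cohort labels. It does not explain leaving out FGF status while the objective and the Cohort C rule remain.

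**The list in Section 12.1 is open-ended, and the protocol's commitments are not withdrawn.** SAP Section 1 describes the SAP as adding detail to the protocol. So a 6-month rate could be read from a Kaplan-Meier table, but only for a column that mixes FGF status. A reader might infer that SAP Section 4 contradicts protocol Section 11.2.1. It does not: Section 4 sets aside cohort enrolment, not FGF status, and protocol Section 11.2.1 itself works within starting dose. The fault is an omission.

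**A reader might infer that pooling could overturn the 10 mg go decision.** The documents do not support this. The planned median decides that rule in every modelled case, and the rule is worded for the 10 mg group as a whole. Pooling takes a passing amplified group to a fail only in narrow cases, for example 40% amplified and 25% non-amplified with m = 34, where the pooled median is 3.99 months. Scans at weeks 4, 12, 20 and 32 (protocol Section 9.5.2.1) cannot resolve such a difference. If progression is seen only at scheduled scans, that case shows an observed median at week 20 (about 4.6 months) and an observed 6-month rate of about 45%.

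**Other SAP outputs are by cohort.** Changes in patient-reported outcomes "will also be given by relevant cohort", and the adverse event list is headed the same way. This wording matches the protocol and looks carried over, so it says little about intent for PFS. PFS is not among those outputs in any case.

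**Conclusion.** The concern holds as a mismatch between the SAP's objective and rules on one side and its planned output on the other. Followed literally, the SAP gives no PFS estimate for amplified patients and no PFS result or 6-month rate with 90% interval for Cohort C. The protocol's FGF comparison and its 6- and 12-month rates are not carried forward. This rests on the text alone.

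The size of the dilution is illustrative. With the assumed rates, the 10 mg 6-month estimate is 5.0 points (m = 20) or 8.3 points (m = 40) below the amplified-only figure. It depends on the assumed rates, on a split the documents do not give, and on no censoring before 6 months. Because this is an estimation study and the 10 mg decision is not shown to change, the point should be fixed but is not critical.

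**What to change.** In SAP Sections 4 and 12.1:
- Add PFS by FGF status (amplified, non-amplified) within starting dose.
- Make amplified patients starting at 10 mg the table for the primary objective, and keep the pooled dose columns as supportive.
- Report the Kaplan-Meier median and the 6-month rate with a 90% interval in each column, and name the interval method.
- Apply the Cohort C rule to the non-amplified 10 mg column.

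If the sponsor no longer wants the Cohort C rule, the SAP should say that it is dropped and why.

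The cost is SAP wording and extra table columns; FGF status, starting dose and PFS dates are already collected. The drawback is smaller columns. If clearly fewer than 40 non-amplified patients started at 10 mg, the Cohort C precision stated in Section 3 may not be reached: at 30 it depends on the interval method, and at 20 it fails under both methods shown. The SAP should acknowledge this. The post-baseline-scan condition in the Efficacy Population (SAP Section 5) is a separate question that this change does not settle.
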